- Not currently participating in a program (personal, e.g., wearing an activity monitor, or structured, e.g., another study) to decrease sedentary time or increase physical activity.
- Not planning to move out of New Mexico within the next year.
- Own a smartphone, tablet or computer OR be willing to use a study provided smartphone capable of running the Fitbit app or website. Additionally, access to the internet or a Wi-Fi hotspot at least once per week is required. Smartphones and data plans will be provided to those individuals who are eligible but do not currently own a computer, tablet or smartphone. Participants loaned a study phone will be asked to sign form indicating they agree to return the phone at the end of the study.
- Availability of a family member or friend to be present (for safety) during remote assessment of physical performance tests.
- Willingness to be randomized to either study arm and to wear activity trackers (activPAL3 [sedentary behavior, standing, stepping] at weeks 1, 13, and 26 for 7 days; the Fitbit activity tracker during weeks 2-26 during waking hours if randomized to the immediate intervention arm; during weeks 14-26 if randomized to the delayed intervention arm).

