8.0 Study Endpoints

Primary endpoints include: a) process data (enrollment, retention and adherence rates; satisfaction with the program), and b) change in self-reported physical function.

Secondary endpoints include change in: a) subjective and objective measures of sedentary- and light-intensity activities, b) physical performance, and c) self-reported quality of life (QOL).

Safety endpoints:

All adverse events associated with the physical performance tests (see section 9.0) will be tracked. The performance tests incorporate movements typically undertaken during normal daily activities (standing from a chair, sitting on a chair), and thus represent tests that are more likely to be safely performed in the home. A friend or family member will be present during the remote assessment of physical performance, which is conducted in the study participants' homes. Safety checks will be made prior to the performance tests (see section 13.0 Potential Risks to Subjects / Protection Against Risks).

Additionally, study participants will be encouraged to report any “emergencies or events” by calling the toll-free study number. See Data Safety and Monitoring Plan for more details.

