Once the study team connects a Fitbit account to Fitabase, Fitabase collects all new data that is collected by the device. When the device syncs (i.e., transfers data), Fitabase is notified of data availability, requests the new data, and then processes the data in order to make it available to the study. The study team will download study participant's de-identified data from Fitabase. Fitabase does not collect personally identifiable data. Each study participant is de-identified with a participant ID. Fitabase does not receive the associated email address, the Fitbit account name, Fitbit Friends list, or any GPS data.

Participants will be given Fitabase's Terms of Use and the Privacy Policy upon request. By consenting to use the Fitbit device as part of this study, the participant also consents to the Fitabase Terms of Use and Privacy Policy. At the end of the study, the participant gets to keep the Fitbit device and will receive instructions how to change the email address associated with the Fitbit account. At the end of the study or if a participant withdraws from the study we will disassociate the Fitbit account from the Fitabase account.

Health Coach Calls / MI: Research assistants will undergo MI training specific to this study. MI techniques and micro-skills will be used to guide five sessions of telephone-based health coaching, which will occur during weeks 3, 5, 7, 9, and 11. Key intervention topics and techniques include: establishing rapport; eliciting knowledge about adverse effects of inactivity/SB and benefits to becoming more active; assessing motivation, confidence, perceived importance and barriers to becoming more active; eliciting change talk; and enhancing participants' self-efficacy (competence) and motivation to be more active (e.g., small, achievable goals). The health coach also provides tech support to the participant for assessments (activPAL and performance testing) and using Fitbit with their mobile app (weeks 1, 2, 13, & 26). The first call (week 2) to help the participant set up their Fitbit may take up to 45 minutes, but can be much shorter depending on the participant's comfort level with technology. The first health coaching call may take up to 45 minutes (week 3); the remaining four health coaching calls will take 20 minutes each (weeks 5, 7, 9 and 11). Health coaching calls will be audio recorded and reviewed for quality control. Audio files will be destroyed 3 years after the study closes.

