Educational Materials: Participants will be mailed educational materials (visual aids) to be used during the telephone calls with their Health Coach. The handouts include: (a) the benefits of LPA and suggestions for how to add more steps to their day, throughout the day (i.e., breaking up sedentary time through at least minimal stepping each hour); (b) reasons to be physically active; (c) example plans for meeting step goals; (d) ideas for getting more steps; and (e) pages for the participant to write their plan for each week. Instructions for setting up and using the Fitbit Inspire 3 tracker and mobile app will be included. All materials serve as reference for discussions with the health coach.

Intervention Fidelity: We will use evidence-based MI training procedures identified in previous studies.^{50,51} The health coaches will receive an initial 1.5 days of in-person MI training by [name] (consultant, clinical psychologist). Prior to contacting participants, the coaches will complete 4 practice sessions, and receive feedback via 4 phone supervision sessions. [name] will code the sessions for MI fidelity by using the MI Treatment Integrity Coding System, version 4.1,⁵² and use this information during supervision sessions. During the study period (15 months), the health coaches will submit one audio recording and participate in one phone supervision per week (months 1-2), then per month (months 3-15). An intervention fidelity checklist will be created to assess the other intervention components, i.e., promoting and supporting self-efficacy, knowledge and skills, self-monitoring, autonomous motivation, and social support to become more active. With HSC Affiliate status, [name] will review the selected audio files saved to the secured P drive.

A Waitlist Control was selected to help boost recruitment and retention. Participants will be asked to maintain their usual lifestyle during the 12-week intervention. After the 12-week waitlist period, participants will receive (via mail) a Fitbit Inspire 3™ monitor and education materials, and the full telephone-based MI intervention with the health coach.

Retention: To enhance recruitment, retention, and adherence rates and to compensate participants for their time and offset phone data charges, a \$50 merchandise card will be provided for each outcome assessment (\$150 total). Additionally, both groups will be able to keep the Fitbit activity tracker after the study ends.

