		X					Reminder to ppt about assessment (text from [name] with link to Zoom or Skype videoconference session for physical function tests)
							Remote assessment conducted / completed via Skype or Zoom

PROTOCOL TITLE: Whole-of-Day Approach to Physical Activity in Older Cancer Survivors

Fees/ Postage	Phone		Email		Mail		
	IN	OUT	IN	OUT	IN	OUT	
		X					Follow-up for incomplete surveys; return of activPAL (see Assessment Call 4 Script ...)
						X	Mail gift card (after verifying activPAL returned, and remote assessment AND surveys completed)
						X	Mail letter to immediate intervention group (maintain usual activity; next study contact in 12 weeks)
							Start intervention for waitlist control participants (Fitbit setup, 5 health coaching calls)
							26-week assessment 
 • Schedule remote assessment w/ [name] via MYHealth calendar • Ask survey preference (mail/online)
							Repeat steps from 13-week assessment
							Post-study telephone survey

NOTES:

¹ Whoever conducts the consent process signs the participants' form once received; for e-consent; print consent form, sign, photocopy and keep one copy in the ppt's folder; mail a copy of signed consent to ppt

² Whoever conducts the consent process signs the participants' form once received; for e-consent; print consent form, sign, photocopy and keep one copy in the ppt's folder, mail a copy to ppt

PROTOCOL TITLE: Whole-of-Day Approach to Physical Activity in Older Cancer Survivors

Outcomes and Measurements

All measures have well-established validity and reliability, and are responsive to change.

Table 2. Outcomes & Measures (B=baseline; P=1-week post-intervention; F=3-months post-intervention follow-up to assess maintenance of behavior change & effects)(alpha=Cronbach's alpha; ICC=intraclass correlation test-retest reliability; RMSEA=root mean square error of approximation; CFI: comparative fit index)	B	P	F
Process Data (primary outcomes): As this is a feasibility and acceptability study, the primary outcomes relate to recruitment, retention, adherence, and adverse events, which will be carefully tracked. Collected and used to evaluate adherence: steps per day/number of active hours (downloaded from Fitbit® website), satisfaction with the program, likes & dislikes, barriers & issues, perceived degree of benefit, and intervention fidelity (see above)		X	X

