PROTOCOL TITLE: Whole-of-Day Approach to Physical Activity in Older Cancer Survivors

classification of accelerometer data. Accelerometer methods will be published according to guidelines.⁸⁰⁻⁸²

Aim 1 - Feasibility & Acceptability: For this feasibility study, we hypothesize that we will meet the accrual target of 64 inactive, older cancer survivors within 18 months, retain 80% of the sample, and to achieve 80% adherence/fidelity to the intervention. No formal statistical analyses are needed for these hypotheses.

Aim 2 - Preliminary estimates of effect sizes: We hypothesize that physical function scores will improve in the intervention group compared to the control group. We will obtain means and precision estimates for between-arm differences in physical function scores at each time point. A linear mixed-effects model will be used with group, time, and group by time interaction, adjusted for ethnicity, rural/urban status, and baseline values as needed. The appropriate variance-covariance structure will be selected to account for the potential correlation among repeated measurements from the same participant. The primary test of interest is the group by time interaction, indicating whether there was a difference between groups in the primary outcome over time. Similar analyses will be conducted for secondary outcomes.

Aim 3 - Process evaluation: will be conducted via a mailed survey. Process data (**Table 2**) and other study related outcomes will be reviewed with the PAB to identify next steps and strategies to ensure the most appropriate design and methods for the future, larger RCT, with potential for broad dissemination and implementation.

PROTOCOL TITLE: Whole-of-Day Approach to Physical Activity in Older Cancer Survivors

Power / Sample Size Calculation

Using a 2-sided, 2-sample t-test, with a significance level of 0.05 and 25 people per arm, we will have 80% power to detect a mean difference of 8.1 in physical function scores (a large effect size) with a standard deviation of 10. To allow for 20% attrition, we plan to enroll and randomize 32 participants per arm. The results of the feasibility trial will inform the design (sample size, effect size) of a larger trial powered to examine efficacy

Maintaining Confidentiality

The following steps will be taken to secure the data and to maintain confidentiality:

- Study participants will be assigned a unique study ID.
- All data collected will be identified with the unique study ID.

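### Do the 80% retention and adherence targets need a planned confidence interval and a stated denominator?

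*Combined protocol and SAP*

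**What the plan says.** Section 8.0 puts the feasibility rates first among the endpoints: "Primary endpoints include: a) process data (enrollment, retention and adherence rates; satisfaction with the program". Sections 1.1 and 10.0 (Aim 1) set 80% for retention and 80% for adherence/fidelity, with 64 participants to be accrued in at most 18 months. Aim 1 then closes with "No formal statistical analyses are needed for these hypotheses".

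The next paragraph, Aim 2, treats the physical function outcome differently: "We will obtain means and precision estimates for between-arm differences in physical function scores at each time point". The sample-size paragraph gives the pilot's purpose: "The results of the feasibility trial will inform the design (sample size, effect size) of a larger trial".

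On adherence, Table 2 in section 9.0 names the data: "Collected and used to evaluate adherence: steps per day/number of active hours". Table 3 sets a goal for active hours, steps above baseline and days per week in each two-week period. Coaching is planned as "five sessions of telephone-based health coaching, which will occur during weeks 3, 5, 7, 9, and 11". After their wait, controls receive a tracker, the education materials "and the full telephone-based MI intervention with the health coach"; section 3.2 has them wearing the tracker "during weeks 14-26 if randomized to the delayed intervention arm".

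On timing, section 7.0 plans 15 months of recruitment in a 2-year study. The Intervention Fidelity paragraph schedules coach recordings and supervision through month 15.

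**The concern.** The plan promises precision for physical function and, by extension, for the secondary outcomes, but none for the rates that decide feasibility. With 64 participants, a narrowly met 80% could be read as retention achieved when true retention might be near 70% or near 90%.

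The definitions also look loose. Adherence could be counted per participant, day, week or call, and in the immediate arm only (32) or in both arms (64). Retention could be taken at week 13 or week 26, and over 64 randomized or up to 70 enrolled. If the choice is made after the data are seen, the same data could give different rates.

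Two timing points came with this. The 18-month accrual criterion and the 15-month recruitment plan are not linked in the text. And the 15 months of coach supervision seem to end before the waitlist arm has been coached, although fidelity is part of the 80% target.

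**Working it through.** **The plan's own figure.** Inputs from section 10.0: 25 per arm, difference 8.1, SD 10, two-sided 0.05. A two-sample t-test then has 80.1% power. Allowing for 20% attrition, 25 / 0.8 = 31.25, so 32 per arm and 64 in total. The stated calculation reproduces.

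**Precision at the 80% line.** The smallest passing counts are 0.8 × 64 = 51.2, so 52, and 0.8 × 32 = 25.6, so 26. The exact (Clopper-Pearson) limits for x of n are the 2.5% point of Beta(x, n − x + 1) and the 97.5% point of Beta(x + 1, n − x).

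| Count | Rate | Exact 95% interval |
|---|---|---|
| 52/64 | 81.3% | 69.5% to 89.9% |
| 56/70 | 80.0% | 68.7% to 88.6% |
| 26/32 | 81.3% | 63.6% to 92.8% |

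The denominators 70 and 32 are assumptions, used to show the range.

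**Chance of observing at least 80%.** This is the binomial tail P(X ≥ 52) for n = 64 and P(X ≥ 26) for n = 32.

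| True rate | n = 64 | n = 32 |
|---|---|---|
| 70% | 3.0% | 11.3% |
| 75% | 15.6% | 27.8% |
| 80% | 47.5% | 53.5% |

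These would be error rates if a decision hung on the 80% line. The plan attaches no such decision. Under Aim 3, process data go to the advisory board to shape the next trial.

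**Retention denominator and time point.** 52 completers are 81.3% of 64 but 52/70 = 74.3% of 70, so the choice could matter. The text points to 64. Section 4.0 replaces people who drop out between consent and randomization, Aim 1 speaks of the sample directly after the target of 64, and the attrition allowance is applied to 32 randomized per arm. Table 2 marks process data at both follow-ups, so both retention rates will be available.

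**Adherence.** Table 2 names tracker steps and active hours as adherence data and says they serve that purpose only. Table 3 gives the goals. What remains open is the share of goals that makes a participant adherent, and whether waitlist participants are counted after crossover. Nothing in the plan defines adherence by calls.

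**Accrual.** Both statements of the criterion word 18 months as an upper limit. Accrual that ends in months 16 to 18 meets the criterion and overruns the plan. The two figures do not conflict.

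**Coach supervision.** Assume even accrual over 15 months, supervision starting with recruitment, waitlist calls shifted by 12 weeks (weeks 15 to 23), and 4.348 weeks per month.
- Last immediate-arm call: 10 to 11 weeks = 2.30 to 2.53 months after entry, so month 17.3 to 17.5.
- Last waitlist call: 22 to 23 weeks = 5.06 to 5.29 months after entry, so month 20.1 to 20.3.
- Entry per arm: 64 / 15 / 2 = 2.13 a month. Participants with calls after month 15: 2.13 × (2.30 + 5.06) = 15.7 to 2.13 × (2.53 + 5.29) = 16.7 of 64. If supervision starts with the first coaching call, two weeks later, this is 13.7 to 14.7.

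The gap concerns only the submitted recordings and phone supervision, which by then run at one per month. The Health Coach Calls paragraph has calls recorded and reviewed for quality control with no end date.

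**The case for a change.** The best case for a change is that the observed attrition feeds the next trial's sample size. For the same 25 analyzed per arm, retention of 69.5% needs 25 / 0.695 = 36.0, so 36 per arm, while 89.9% needs 25 / 0.899 = 27.8, so 28. On that view the interval is a design input, and one sentence would supply it at no cost. Fixing the adherence definition before results are seen would also remove any temptation to choose the flattering one.

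The first part is true but gains nothing. The interval follows from the counts, which a feasibility report has to give, and the Aim 1 sentence declines formal analysis of the hypotheses without barring a descriptive interval. Whoever designs the larger trial can compute it in a line.

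The second part is the strongest of what remains. The adherence unit is undefined, and adherence is reported together with fidelity. But asking that denominators and time points be stated does not itself settle what makes a participant adherent. The data source and the weekly goals are already fixed, which leaves analysts limited and visible choices.

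On supervision, the mismatch between the 15 months and the delivery period stands as a small inconsistency. Closing it might add about five months of monthly supervision, for calls that the general quality review already covers.

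**Conclusion.** The concern is correct in its facts and too strong in its conclusion. No interval is promised, the adherence unit is open, and the retention target is not tied to one visit. At 80% the exact intervals run from about 70% to 90% with 64 participants and from about 64% to 93% with 32.

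No change follows, because the 80% figures carry no test and no decision rule, the intervals can be had from the counts, 64 randomized is the evident retention base with both follow-ups recorded, and Table 3 gives the content of adherence. A sensible analyst would report retention at week 13 and at week 26, and adherence per participant against the Table 3 goals, each as a count over its denominator.

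The accrual point falls away, since 18 months is a ceiling. The supervision period is a minor scheduling mismatch, touching about 14 to 17 of 64 participants under the even-accrual and mirrored-call assumptions above, and it leaves the analysis as it is.

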1.1 Primary Aims and Hypotheses

1.1.a. Determine the feasibility and acceptability of a home-based lifestyle activity intervention by assessing recruitment, retention, adherence rates, and participant satisfaction, and monitoring adverse events. We hypothesize that we will meet the accrual target of older cancer survivors within 18 months, retain 80% of the sample, and achieve 80% adherence/fidelity to the intervention with high satisfaction ratings, while limiting the number of adverse events.

1.1.b. Estimate effect sizes for primary and secondary endpoints for the adoption (baseline to 12 weeks) and maintenance (3-months post-intervention) of the intervention. We hypothesize that compared to the control condition, the intervention will result in improvements in physical function (primary outcome) and secondary outcomes: physical performance, objective measures of sedentary- and light-intensity activities, and self-reported quality of life. Further, we hypothesize that the arm differences at 12 weeks will be sustained at 3-months post-intervention.

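### The primary test, a group-by-time interaction with baseline adjustment left open, depends on week 26, when the waitlist arm has been treated, and is not the week-13 comparison of intervention with no intervention

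*Combined protocol and SAP*

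**What the plan says.** The Aim 2 paragraph of section 10.0 specifies a linear mixed model with group, time and their interaction, "adjusted for ethnicity, rural/urban status, and baseline values as needed". It continues: "The primary test of interest is the group by time interaction", "indicating whether there was a difference between groups in the primary outcome over time". It does not name a visit or contrast, list the levels of time, or say whether baseline is a response or a covariate. The same paragraph also promises estimation by visit: "We will obtain means and precision estimates for between-arm differences in physical function scores at each time point".

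Other parts of the protocol bear on this:

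- Section 8.0 defines the endpoint as "change in self-reported physical function".
- Section 1.1 adds a maintenance hypothesis: "we hypothesize that the arm differences at 12 weeks will be sustained at 3-months post-intervention".
- Section 9.0 (Waitlist Control) gives that arm, after its 12-week wait, a Fitbit, the education materials "and the full telephone-based MI intervention with the health coach". Section 3.2 dates its Fitbit wear to weeks 14-26, and the study-flow table starts its intervention after the 13-week assessment and before the 26-week one.
- Table 3 gives the immediate arm no study contact in weeks 14-25.
- The power statement rests on a single comparison: "Using a 2-sided, 2-sample t-test, with a significance level of 0.05 and 25 people per arm".

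**The concern.** Randomization gives a comparison of intervention with no intervention only up to week 13. At week 26 the comparison is immediate intervention (followed by 12 weeks without contact) against delayed intervention (just delivered). That difference could shrink to zero or favour the waitlist arm even if the intervention works.

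A group-by-time interaction over these visits is therefore not a test of the week-13 effect, and what it does test depends on a choice the plan leaves open:

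1. **Baseline as a response.** This is the more natural reading, given that the endpoint is a change and the test concerns differences over time. With categorical time, it is an unsigned 2-df test that the arm differences in change at weeks 13 and 26 are both zero.
2. **Baseline as a covariate.** Only weeks 13 and 26 are then responses, and the interaction is a 1-df test that the week-26 difference equals the week-13 difference. A sustained effect, which is what section 1.1 hypothesizes, is its null hypothesis.

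The result labelled primary could thus be significant with no week-13 effect, or null when the hypothesized effect is real. Either could sit beside week-13 estimates that say something different, in a pilot meant to inform the effect size and sample size of a larger trial.

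**Working it through.** **Inputs from the plan (section 10.0):** n = 25 evaluable per arm, SD 10, difference 8.1, two-sided alpha 0.05. **Assumptions:** the documents give no between-visit correlation, so r = 0.3, 0.5 and 0.7 are used. Covariance is compound symmetry with equal SDs unless stated.

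**Step 1: the plan's own figure.** The noncentrality of the two-sample t-test is 8.1 / (10 × √(2/25)) = 2.86 on 48 df. This gives 80.1% power and a detectable difference of 8.09. The stated 80% for 8.1 reproduces, but it belongs to a comparison at one time point.

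**Step 2: the three tests.** Let a and b be the true arm differences at weeks 13 and 26, with no baseline difference.

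- *Interaction, baseline as response:* Hotelling test on the two change scores, noncentral F(2, 47), λ = (a² − ab + b²) / (12(1 − r)).
- *Interaction, baseline as covariate:* two-sample t-test on week 26 minus week 13 (48 df), squared noncentrality (b − a)² / (16(1 − r)).
- *Baseline-adjusted week-13 contrast:* noncentral t on 47 df, noncentrality a / (10 × √(1 − r²) × √(2/25)).

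Worked examples at r = 0.5:

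- For a = 0, b = −5: λ = 25/6 = 4.17, so the response-coded test rejects in 40.7%. For the covariate-coded test, 25/8 = 3.12, giving 41.0%.
- For a = b = 8.1: λ = 65.61/6 = 10.9, giving 82.5%. The covariate-coded noncentrality is 0, giving 5.0%. The week-13 contrast has noncentrality 8.1/(8.66 × 0.283) = 3.31, giving 89.9%.

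**Step 3: rejection rates (%) at r = 0.3 / 0.5 / 0.7.**

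| True difference, week 13 then week 26 | Interaction, baseline as response | Interaction, baseline as covariate | Adjusted week-13 contrast |
|---|---|---|---|
| 0 then −5 | 30.2 / 40.7 / 62.2 | 31.0 / 41.0 / 60.9 | 5.0 |
| 8.1 then 8.1 (sustained) | 67.7 / 82.5 / 96.7 | 5.0 (type I error) | 83.7 / 89.9 / 97.5 |
| 8.1 then 0 (full catch-up) | 67.7 / 82.5 / 96.7 | 66.0 / 80.1 / 95.2 | 83.7 / 89.9 / 97.5 |
| 8.1 then 4.05 (r = 0.5 only) | 69.9 | 28.9 | 89.9 |

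Under response coding, the sustained and full catch-up rows are identical because a² − ab + b² = 65.61 in both. A significant result cannot say which occurred.

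**Step 4: sensitivity of the response-coded test (r = 0.3 / 0.5 / 0.7).**

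- AR(1), SD 10: 26.3 / 33.4 / 50.3% for 0 then −5; 60.4 / 72.9 / 91.0% for sustained 8.1.
- Baseline SD 5, compound symmetry: 35.2 / 45.1 / 63.6% for 0 then −5; 90.4 / 94.9 / 98.2% for sustained 8.1.

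The value 5 comes from section 3.2, which describes eligibility as 0.5 to 1.5 SD below the population mean. That is a band of 10 T-score points, and scores confined to it have an SD of at most 10/2 = 5.

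A simulation with 8,000 replicates and an estimated baseline slope gave 30, 41 and 62% (response), 31, 42 and 61% (covariate) and about 5% (week 13) for 0 then −5. For sustained 8.1 with baseline SD 5 it gave 90, 95 and 98% (response) and 83, 89 and 97% (week 13).

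**The case against.** The strongest reply is that the harm is limited and partly hypothetical.

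- *The 0 then −5 case is strained.* Both arms get the same package, so if it did nothing for one arm there is little reason for it to yield 5 points in the other. Decline in the immediate arm alone is possible, but the documents do not suggest it. This is fair, and the case is used only to show what the test responds to. The sustained-effect result under covariate coding needs no such scenario.
- *The interaction often detects a real effect.* This is true under full catch-up, where both codings come close to the planned 80.1% at r = 0.5, and under response coding with a sustained effect. With a baseline SD of 5 and r = 0.3 to 0.5, the joint test even beats the adjusted week-13 contrast (90% and 95% against 84% and 90%). Baseline questionnaires follow the eligibility screen, so 5 is not a firm cap on the baseline SD. The case for week 13 therefore rests on which question is tested, not on a guaranteed gain in power.
- *Per-visit differences are already planned, and no decision is tied to the interaction p-value.* This is correct. The week-13 estimate is not lost, which limits the severity.
- *Other readings exist.* With only baseline and week 13 in the model, the interaction would be the week-13 difference in change. No text limits the model that way, and the promise of estimates at each visit points to all three. Linear time would also depend on week 26: under full catch-up it rejects in about 5% despite an 8.1-point effect at week 13.
- *A joint test suits a hypothesis of effect plus persistence.* It suits it only loosely, because the waitlist arm is no longer untreated when persistence is assessed.

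**Conclusion.** The concern holds and should be fixed. Under either usual coding, the designated primary test depends on a visit at which both arms have been treated, and the open baseline adjustment leaves the choice between two different hypotheses unmade. In the covariate form, the effect hypothesized in section 1.1 is the null, with 5% rejection whatever the correlation. In the response form, a significant result does not establish a week-13 effect.

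These structural points follow from the design and need no assumed correlation. The 5% also needs no particular SD, whereas the other rejection rates are illustrations at assumed correlations and covariance structures. The sample size is not shown to be wrong: the 25 evaluable and 32 randomized per arm stand.

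**What to change.** In the Aim 2 paragraph of section 10.0:

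1. Name the week-13 between-arm difference in PROMIS Physical Function T-score, with 95% CI, as the primary contrast, from the planned mixed model with categorical time.
2. Always include baseline, either as a covariate with post-baseline responses or through a constrained common baseline mean. Always include ethnicity and rural/urban status. Delete the words that make adjustment optional.
3. Report the week-26 difference as a secondary contrast, described as immediate versus delayed intervention.
4. State that the 8.1 detectable difference refers to the unadjusted week-13 comparison. It is likely conservative after baseline adjustment: 8.09 × √(1 − r²) gives 7.7, 7.0 and 5.8 at r = 0.3, 0.5 and 0.7.

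The cost is a few sentences, with no new data, visits or participants. The one real trade-off is that the joint test over the adoption and maintenance visits is no longer primary. It has more power in some settings, such as a sustained effect with a narrow baseline SD, so the team should make this choice of estimand knowingly.
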